5.3 Other Outcomes of Interest

Cognitive deficits in MDD are consistent, replicable, nonspecific and clinically significant. Pronounced deficits in executive function (≥ 1 SD below the normative mean) are evident in about 20-30% of individuals with adult MDD. A recent meta-analysis of children and adolescents with MDD demonstrates that they perform 0.194-0.772 ($p < 0.001$) standardized mean differences worse than healthy controls in neuropsychological test procedures. The most pronounced deficits of children and adolescents with MDD were seen in inhibition capacity ($SMD = 0.772$; $p = 0.002$), phonemic verbal fluency ($SMD = 0.756$; $p = 0.0001$), sustained attention ($SMD = 0.522$; $p = 0.000$), verbal memory ($SMD = 0.516$; $p = 0.0009$) and planning ($SMD = 0.513$; $p = 0.014$) [210], with some conflicting results [211]. Other replicated abnormalities are in the domains of working memory, attention, and psychomotor processing speed. Cognitive deficits may account for the largest percentage of variance with respect to the link between psychosocial dysfunction (notably workforce performance) and MDD [212]. We expect that those with the lowest omega-3 index and the highest omega-6/omega-3 index will have the most severe impairments in cognition. We expect that those patients are the ones that benefit most from omega-3 fatty acids.

5.4 Safety Outcomes

WH 5a – We hypothesize that Omega-3 fatty acids treatment will be a safe treatment with no drug-related SUSARs, in particular with no increase in suicidal ideation (SIQ-Jr).

6 STUDY DESIGN AND COURSE OF STUDY

6.1 General Study Design and Justification of the Design

We will apply a 36week, multi-centre, double-blind, placebo-controlled, fixed dose, parallel group design to study the efficacy of Omega-3 fatty acids on pMDD. The double blind RCT includes a 12week acute treatment phase and a 24 week maintenance phase. A single-blinded placebo-run in phase will try to minimize the initial placebo response and contribute to the elimination of false positive inclusions in rapid placebo responders. In order to do this reliably, 220 patients aged 8 – 17 years with a primary diagnosis of depression will be randomly allocated to receive a daily dose of omega-3 fatty acid (500mg EPA / 250 mg DHA for the 8 < 13 years old; 1000mg EPA / 500mg DHA for the 13 < 18 years old) or matching placebo capsules for 36 weeks. A study of this size should have enough power to detect whether omega-3 fatty acid is an efficient treatment for pMDD.

[figure not shown]

After written consent and extensive screening of the patients, the 7 to 10 days placebo lead-in phase will commence. After completion of the placebo lead-in phase, the Children's Depression Rating Scale (CDRS-R) will be applied to determine whether the patients still fulfill the criterion of a moderate depression (score > 40), and then the patient will be randomly assigned to a study group. After an extensive baseline examination, subsequent assessments will occur at 6 weeks, 12 weeks, 24 weeks and 36 weeks. At each assessment depressive symptoms and other psychological variables will be assessed using a variety of different rating scales. Assessment of cognitive functioning occurs at baseline, week 12 and week 36. Blood, urine and saliva will be taken at the screening visit and after 12 and 36 weeks.

Assignment to a treatment arm will be performed randomly to eliminate the possible influence of arbitrary allocation of subjects on the study results. Using random assignment, known and currently unknown factors potentially influencing outcomes (e.g. demographic factors, findings at screening examination) are evenly distributed among the two groups, which increases the validity of statistical analyses. Administration of medication will be double-blind in order to minimize the influence of expectancy regarding the type of medication on data collection and analysis. A placebo arm is included as the effectiveness of omega-3 fatty acids in the treatment of depression will be examined, and no other psychopharmacological treatment is recommended in pMDD in children and adolescents. All the children will receive concomitant standard treatment as advised by their clinicians.

The study examines the effectiveness of omega-3 fatty acids in children aged 8-17 years old. Inclusion of minors is essential as no current pharmacological treatment for pMDD exists and data of adults might be not transferrable as fatty acids have been implicated in the process of adolescent brain maturation.

6.2 Study Duration and Study Schedule

Our recruitment goal is to include 220 patients with at least one follow-up assessment in the trial. Until now, we have randomized 225 patients. However, 21 patients dropped out before reaching the first follow-up assessment and thus, these need to be replaced. Therefore, we will need to randomise another 20 patients in order to reach our target of 220 patients with at least one follow-up assessment. We estimate that we will reach this target in May 2021. In addition, we will recruit up to 20 additional patients to account for the ones who started antidepressant treatment within the first 6 weeks of the trial. This will give more power to our a priori-defined analyses in which start of antidepressant treatment will count as a drop out criteria. The intention-to-treat analyses will still include all patients who were enrolled in the trial. Last follow-up assessments will then be carried out in March 2022 at the latest. After, we will close the database and start analysing the data set.

6.3 Methods of Minimising Bias

6.3.1 Randomisation

The active and maintenance treatment phase consists of a 1:1 randomized placebo-controlled allocation sequence for the 36-week study period. A dynamic computerized 1:1 randomisation stratified for age, gender, type of treatment (in- or outpatient) and hsCRP across each site will be applied. A minimisation algorithm integrated in SecuTrial® will provide a balanced distribution between the two treatment groups (active/ placebo) for each site and strata.

Access to the SecuTrial® generated randomisation list will be restricted to the Clinical Trial pharmacist, in case of an interim analysis to the IDMC, upon request to the regulatory authorities

and to the data management at the USZ CTC. The study medication will be labelled at the KAZ and will be sent out to the study sites in two batches.

The algorithm and allocation process is implemented in SecuTrial and the development of the algorithm is done by the data manager of the Clinical Trial Centre and cannot be influenced by the investigators. The clinicians and researchers who enrol the patients just provide the relevant stratification data. The minimization algorithm contains an element of chance so that even with the knowledge of all previous allocations the next allocation cannot be determined.

Participants, parents, treating clinicians and doctors, research assistants, all involved researchers including the PI remain blind to the allocation of participants to the study drug (active/ placebo). SecuTrial® only provides one single randomisation number making it impossible to guess the allocation. Data analyst (PD Dr. rer. nat. [name], [name]) will only get access to the randomisation code list after completion of data entry, double entry of a subset of data and final closure of the database. The only person who has access to the computer-generated allocation code is the data manager of the CTC and the clinical trial pharmacist of the Clinical Trials Pharmacy of the Universities of Zürich (*Kantonsapotheke Zürich KAZ*).

If deemed necessary, the IDMC is allowed to review unblinded data as further specified in the IDMC SOP.

6.3.2 Other Methods of Minimising Bias

Based on two comprehensive meta-analyses on placebo-response [188, 189] and a RCT comparing fluoxetine versus placebo in pMDD with a low placebo-response [206] we implemented a number of measures to minimize the placebo-response:

- As the number of sites is a strong predictor of placebo-response, we have limited the number of sites (the lead centre (ZH), one additional academic centre (BS), as well as three further Cantons (TG, SG, BL) in the proximity of the lead centre (ZH)). Many of the senior clinicians in the regional centres were trained or worked as consultants in the academic lead centre (ZH). Furthermore, the academic and non-academic centres have a joint training program for their trainees for several years providing a good foundation that all participant will undergo a similar treatment approach.
- We will implement regular meetings with therapists from the participating centres to improve adherence with the S3 guidelines.
- The number of research assessments has also been identified as a predictor for placebo-response [188, 189]. We have limited the research assessments to three assessments during the active treatment phase (baseline, 6 and 12 week), and two further assessments in the maintenance phase (24 and 36 week), what is much lower than in comparable trials.
- Based on previous RCTs in pMDD [213], we expect a 10-20% drop in overall CDRS-R score during the 7-10 days placebo-lead in phase. If a participant drops below a CDRS-R total score <40 at the end of the placebo lead in phase, the participant will not be enrolled in the double-blind randomized study period (as he does not meet inclusion criteria anymore). Similar strategies were already applied in other RCTs of pMDD and could attenuate placebo response and eliminated false-positive enrolments (a participants that has such a dramatic decrease in symptom load within the placebo lead-in phase is unlikely to suffer from “true MDD”, but more likely from an adjustment disorder) [213, 214]. We will

offer placebo-responders to be followed up separately as a non-randomized comparison group to better understand the characteristics of such placebo-responders (an important “by-product” of the proposed study [215]). Finally, to reduce the likelihood that a site can estimate a possible allocation sequence, we will not provide stratification blocks to the clinicians (see allocation concealment) [206].

- To avoid a selection bias, we decided to allow the use of SSRIs as clinically required. Elsewise, we would probably not be able to include a representative sample of moderately or severely ill children meeting criteria for major depressive disorders. However, the latter may result in an unequal distribution of antidepressant use between the treatment arm and increase the response rate across both treatment arms, making it less likely to address the primary aim of the study. To address this flaw of the study design, we decided to include a further a priori defined analysis approach: We will analyse the primary outcomes using “start of an antidepressant medication” as a “drop out criteria” and jointly model the longitudinal CDRS-R score and the time to study drop out. This will allow us to investigate if omega-3 fatty acids as a sole treatment have antidepressant activity or not. As interim analyses showed that about 20 of our patients started antidepressant treatment within the first 6 weeks (prior to the first follow-up assessment), we will recruit up to 20 additional patients to gain more power for our secondary analyses.

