In the field of lipid research, increasing evidence is emerging that pro- and anti-inflammatory mediators are of pivotal importance for brain development, synaptic plasticity and brain functioning [62, 63, 101, 205]. The identification of inflammatory and/or bioactive lipid markers that are predictive for omega-3 fatty acids response might open up new treatment targets for future drug development for MDD. Our study includes the a priori hypothesis that in particular pMDD cases with elevated inflammatory mediators may benefit from omega-3 fatty acids treatment. If such an approach can be proven, the measurement of such markers will identify omega-3 fatty acids responsive patients contributing towards a personalized and evidence-based decision-making process to indicate who might benefit at what point from the use of EPA-rich omega-3 fatty acids – and possibly even more importantly, under what conditions omega-3 fatty acids are not helpful.

The relationship between important psychopathological features such as suicidal ideation or overt aggression and bioactive lipids is another more explorative aim of the study that may help to further characterize subgroups of pMDD at increased risk of harm, a group of subjects where early detection and monitoring is critical.

The establishment of a BioBank in accordance with the Swiss HFG/KlinV/HFV regulations of this well-characterized patient population with medium-term follow up data will enable further exploration of identified candidate biomarkers at a gene and protein level. There are very few tissue repositories of pMDD or first onset depression cases. In our pMDD sample effects of chronicity of illness and past treatments are minimized enabling the investigation of the underlying neurobiology with minimal confounders. The resulting tissue repository will therefore become a source for other researchers to investigate the underlying causes and dysfunctions of pMDD and MDD. The repository will be open to the wider research community in accordance with the Swiss HFG/KlinV/HFV regulations.

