8.7.3 Use of sedative medications (Benzodiazepine, antipsychotics)

The use of subtherapeutic doses of antipsychotic medication (e.g. 100-200mg quetiapine, or up to 2mg of risperidone) is permitted in case of medically required behavioural control (i.e. significant worsening of behavioural problems in an inpatient setting) at study entry, as well as during the study as long as it is not prescribed for one of the listed conditions under exclusion criteria.

Use of benzodiazepines is not limited or directed by the protocol. Subjects who start using or continue using PRN benzodiazepines (e.g. Temesta® for anxiety, or Stilnox® for sleeping) can

do so. Existing prescriptions of other psychiatric medication is evaluated at baseline and continued if clinically indicated (e.g. stimulant treatment of a longstanding ADHD). We will compare the duration and dose of concomitant (PRN) medication between active and placebo, a further secondary outcome measure.

All concomitant and/or rescue treatment(s) will be recorded in the eCRF.

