5.2 Secondary endpoints

5.2.1 Confirmatory secondary endpoints

- Remission (CDRS-R total score less than or equal to 28) at any point during the 36 weeks of trial observation
- Response (30% reduction in CDRS-R total score) at any point within 12 weeks from baseline
- Participants newly initiating antidepressant medication (or newly increasing dose if on antidepressant at baseline) at any point during the 36 weeks of trial observation
- Number of days on trial before new antidepressant initiation (or new antidepressant dose increase if on antidepressant at baseline)
- KIDscreen-CAT-27 overall quality of life score at 36 weeks
- DIKJ depression score at 36 weeks

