Missing data By design, several baseline model covariates cannot be missing, as they are required for minimization during randomization. We distinguish between study dropouts and intervention dropouts. Study dropouts are participants whom withdraw consent, are monotone not available for follow-up visits, or are removed from the trial according to the protocol due to non-compliance (< 60% pills taken). Intervention dropouts are participants whom newly initiate an off-trial antidepressant or are newly prescribed an increased dose of an off-trial antidepressant prescribed before baseline.

Methods to handle missing data are outlined per analysis type below. Where multiple is used, 50 imputed datasets will be computed. Results across datasets will be combined using Rubin's rule.

Modeling In case of covariate imbalance on baseline covariates other than antidepressant use, omega-3 index, age, gender, and hsCRP, these covariates will also be included in the models described below. In case of computational convergence issues, simpler models will be estimated.

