7.1.2 Sensitivity analyses for the primary endpoint

1. **Typical ITT analysis:** In order to compare results with other trials, the linear mixed model part of the analysis model above will be applied to the full analysis set, with all participants analyzed as randomized. The data from intervention dropout participants will be used as observed, i.e, the outcomes observed while on non-randomized antidepressants will be used. The mixed model assumes that missing data is missing at random. This analysis is expected to be biased toward the placebo arm, as the number of participants requiring antidepressants is expected to be higher in the placebo arm and the additional antidepressant will improve outcomes.
2. **Modified ITT analysis:** The first sensitivity analysis will be repeated, but the data from intervention dropout participants will be considered missing in the mixed model upon non-randomized antidepressant initiation/dose increase. The responses of participants with missing data will be assumed similar to those with complete data and similar covariate characteristics. The bias resulting from imbalance in the use of non-randomized antidepressants across treatment groups is curtailed, but the amount of data available for analysis, and therefore power, is diminished.
3. **Typical PP analysis:** In order to address the efficacy estimand, the sensitivity analysis model above will be applied to all full analysis set data during which participants were 'on protocol'. This means the participants are adhering to the treatment they were randomized to and are not using additional antidepressants. Non-compliers and those taking non-randomized antidepressants are excluded completely (i.e., complete case analysis). This yields an estimate of efficacy that is unbiased under the MAR assumption. It assumes that participants with missing data (those with additional antidepressants and those not adhering to randomized treatment) would have had similar outcomes to participants completing the study in the same treatment arm and with similar baseline characteristics and score trajectories. However, the use of additional anti-depressants is not considered to be random across participants, but rather related to intermediate outcomes and possibly treatment assignment. Selection bias is then expected to affect this estimate. Additionally, the reduction in participants decreases the power to detect a treatment effect.

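### The antidepressant-censored analyses keep patients on an unchanged antidepressant from baseline, so they do not isolate the effect of omega-3 without an antidepressant

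*Protocol*

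**What the plan says.** Protocol 6.3.2 permits antidepressants during the trial: "To avoid a selection bias, we decided to allow the use of SSRIs as clinically required". To deal with unequal use between arms, it adds an analysis in which starting an antidepressant counts as drop-out and is modelled jointly with the CDRS-R score. Its stated purpose is: "This will allow us to investigate if omega-3 fatty acids as a sole treatment have antidepressant activity or not". The same section, with Protocol 6.2 and 8.7.2, gives these analyses as the reason for up to 20 extra patients.

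The eligibility lists (Protocol 7.1.1 and 7.1.2) contain no criterion on antidepressant use at entry. The SAP plans for baseline users. Its endpoint on new antidepressant use (5.2.1) has a separate clause for them, "or newly increasing dose if on antidepressant at baseline". The paragraph on missing data in SAP section 7 defines the censoring event: "Intervention dropouts are participants whom newly initiate an off-trial antidepressant or are newly prescribed an increased dose of an off-trial antidepressant prescribed before baseline". The primary joint model (SAP 7.1) censors at that event, and the modified ITT analysis (SAP 7.1.2, item 2) uses the same one: "the data from intervention dropout participants will be considered missing in the mixed model upon non-randomized antidepressant initiation/dose increase". Baseline antidepressant use is a covariate in the longitudinal model.

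**The concern.** An analysis that is to show what omega-3 does without an antidepressant should rest on scores recorded without one. The censoring rule removes scores after a change in antidepressant treatment. It does not remove scores recorded on an antidepressant that was running at baseline and was not increased. A patient who starts the day before baseline and stays on that dose contributes at every visit; one who starts the day after is censored.

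At stake is how the result is read. If omega-3 acts differently with and without a concurrent antidepressant, the censored analyses give an average of two effects, and the sentence in Protocol 6.3.2 attributes that average to one of them.

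**Working it through.** **1. What the rule does to each kind of patient** (SAP section 7 on missing data, 7.1, and 7.1.2 item 2), assuming no study dropout:

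| Antidepressant at baseline | Afterwards | Event? | Scores used in joint model and modified ITT |
|---|---|---|---|
| No | Never started | No | All five visits, without an antidepressant |
| No | Started | Yes | Up to the start, without an antidepressant |
| Yes | Dose increased | Yes | Up to the increase, on an antidepressant |
| Yes | Dose not increased | No | All five visits, including those on an antidepressant |

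The last row is the main gap. The third row also contributes on-antidepressant scores before its event.

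**2. What the covariate does.** In SAP 7.1 baseline antidepressant use has one coefficient and no interaction with treatment or time. The reported week-36 effect (intervention term plus its week-36 interaction) is therefore common to users and non-users. The covariate adjusts for a difference in level; it does not separate two treatment effects.

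**3. Whether another planned analysis fills the gap.**
- Subgroup analysis (SAP 7.1.1): omega-3 index only.
- Per-protocol (SAP 7.1.2 item 3): it refers both to additional antidepressants and to non-randomised ones. The first term leaves baseline users in; the second can be read as taking them out. The counterpart in Protocol 11.4.1 removes those who initiate additional antidepressants, which leaves baseline users in. The SAP itself expects selection bias and lower power in this set.
- Delta-based imputation (SAP 7.1.2 item 4): delta is added only for intervention dropouts, so the scores of unchanged-dose users stay as observed.
- Secondary estimand (SAP 4.2): it assumes adherence to randomised treatment and does not define an antidepressant-free population.

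**4. Illustrative size.** The plan gives no figure for this point. As a check on the method, the two-sample t-test for SMD 0.54 at 90% power gives 73.04, that is 74 per arm, as SAP 6.1 states.

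Inputs: effect without an antidepressant d0 = 0.40 (the smaller SMD in SAP 6.1); 110 per arm (Protocol synopsis); two-sided 5% level. The share q on an antidepressant at baseline and the add-on effect d1 are assumptions. With q equal in both arms,

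estimate ≈ (1 − q) × d0 + q × d1.

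For q = 20% and d1 = 0: 0.80 × 0.40 + 0.20 × 0 = 0.32.

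| q | d0 = 0.40, d1 = 0 | d0 = 0.40, d1 = 0.20 | d0 = d1 = 0.40 | d0 = 0, d1 = 0.40 |
|---|---|---|---|---|
| 5% | 0.38 | 0.39 | 0.40 | 0.02 |
| 10% | 0.36 | 0.38 | 0.40 | 0.04 |
| 20% | 0.32 | 0.36 | 0.40 | 0.08 |
| 30% | 0.28 | 0.34 | 0.40 | 0.12 |

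**5. What restriction costs.** Limiting the set to patients without an antidepressant at baseline leaves 110 × (1 − q) per arm. Power of the t-test (noncentrality d × √(n/2)), ignoring censoring, dropout and repeated measures:

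| q | n per arm, restricted | Restricted, SMD 0.40 | Full set, d1 = 0 | Full set, d1 = 0.40 |
|---|---|---|---|---|
| 5% | 104.5 | 82.1% | 80.1% | 84.0% |
| 10% | 99 | 80.0% | 75.7% | 84.0% |
| 20% | 88 | 75.1% | 65.6% | 84.0% |
| 30% | 77 | 69.4% | 54.3% | 84.0% |

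For q = 20%: restricted 0.40 × √44 = 2.65; full set with d1 = 0, 0.32 × √55 = 2.37; full set with equal effects, 0.40 × √55 = 2.97. Restriction gains power if the add-on effect is zero and loses some if the effects are equal. The reason to restrict is interpretation.

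**The case against.** Several stronger readings are tempting, and the documents do not support them.

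- *Baseline users are never censored.* They are, at a dose increase: the SAP's event includes those who "are newly prescribed an increased dose of an off-trial antidepressant prescribed before baseline".
- *The trial cannot say anything about omega-3 without antidepressants.* That goes too far. SAP 7.2.1 applies the term non-randomised antidepressant to drugs taken at baseline, so the per-protocol item can be read as excluding baseline users. The wording is ambiguous; the analysis is not plainly absent.
- *The primary comparison is biased.* Baseline use precedes randomisation, so it does not bias the contrast between arms in expectation. It is a covariate and is to be summarised by arm. That it is not a minimisation factor changes little.
- *The trial's objective is misstated.* SAP 3 and 4 already describe omega-3 as an adjunct to guideline care; the sole-treatment wording is a sentence in the protocol. The first-line label does not require that nothing else is given: Protocol 3.7 uses it for a first step within a wider treatment plan.
- *The protocol promises a sample with little past treatment.* The sentence "In our pMDD sample effects of chronicity of illness and past treatments are minimized" concerns the tissue repository and makes no claim about the censored analysis.

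Two further objections stand in full. First, removing baseline antidepressant users would still not make omega-3 a sole treatment: all patients receive background care based on cognitive behavioural therapy (Protocol 8.7), and Protocol 8.7.3 allows other psychotropic drugs and says "Existing prescriptions of other psychiatric medication is evaluated at baseline and continued if clinically indicated". Second, the size is not anchored. The figure of around 30% in both documents is additional antidepressant use during follow-up. A zero add-on effect is the extreme case among those with an effect in the same direction, and Protocol 3.4.2 cites two trials pointing to a possible augmentation effect.

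What remains is that patients on an unchanged dose stay in the analyses meant to show the effect without an antidepressant, and no analysis clearly separates them.

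**Conclusion.** The point holds in limited form. As specified, the joint model and the modified ITT analysis estimate the effect of omega-3 without newly started or increased antidepressants, averaged over patients with and without one at baseline. The property claimed in Protocol 6.3.2 is not delivered as written. The adjunct conclusion that the SAP aims for is unaffected.

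The size cannot be fixed from the documents. It depends on the baseline share and on how far the add-on effect differs from the effect without an antidepressant. In the illustration it is slight at 5% and material at 20% to 30% if the add-on effect is zero; it vanishes if the effects are equal. If only the add-on effect exists, the full set would show a small effect that does not occur without an antidepressant. The plan should be changed because the data needed are already collected and the reported result can then be matched to the right population.

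**What to change.** 1. In SAP 7.1.2, add a prespecified supportive analysis: rerun the joint model and the modified ITT analysis in participants not taking an antidepressant at baseline, still censored at first start. Because the restriction uses a pre-randomisation variable, it keeps the randomised comparison, unlike the per-protocol set.
2. In the full set, report the treatment contrast by baseline antidepressant use (yes or no) with confidence intervals, and the baseline share by arm.
3. State in SAP 7.1.2 item 3 whether the per-protocol set removes patients taking an antidepressant at baseline.
4. Replace the sole-treatment wording. For the full set: *without newly started or increased antidepressants, as an adjunct to S3 care*. For the restricted set: *without antidepressants, as an adjunct to S3 care*.

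The cost is SAP text and a restricted rerun on data already required for the model. The downside is fewer patients and a wider interval in that analysis: the standard error grows by about 1/√(1 − q), for example 1/√0.80 = 1.12 at an assumed share of 20%. The primary analysis, recruitment and patient treatment do not change.
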